8.4.7 Sub-Group Analyses

None will be performed because of the small size of the study.

8.4.8 Tabulation of Individual Participant Data

No individual participant data will be tabulated.

8.4.9 Exploratory Analyses (Immune Responses)

Exploratory immune analyses will be conducted to evaluate anti-tumor immune responses induced by vaccine injections. Immune response will be assessed among all subjects treated in each dose level. The magnitude of immune responses will also be described. A subject will be considered evaluable for immune response if they receive at least three vaccine injections. The percentage of subjects with a positive immune response will be evaluated by dose levels and overall enrollment. A positive immune response is defined by CMI reactivity in *ex vivo* stimulation using a flow cytometric readout (cytokine production or CD107 expression). Antigen-specific peptide challenge assays require a readout of >250 reactive T-cells/million cells above the background (35).

If more than one dose level of patients is enrolled and at least three patients are treated in the dose level, Statistical analyses of data will be performed. For flow cytometry analyses on PBMC samples, Student T tests will be performed on percentages of TNF- α and/or IFN- γ expressing cells among the different dose levels to determine any significant differences in cell populations.

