1.1.3 Exploratory Objectives

To evaluate the ability of the combination ETBX-011, ETBX-051, ETBX-061 vaccine regimen to generate T-cell responses specific for Brachyury, MUC1, and CEA.

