5.1.6 Sample Analysis

Immune assessments will be performed at the Laboratory of Tumor Immunology and Biology at the NCI's Center for Cancer Research (CCR) and include flow cytometry-based and serum assays.

Analyses of PBMCs:

1. Pre- and post-therapy PBMCs, separated by Ficoll-Hypaque density gradient separation, will be analyzed for antigen-specific immune responses using an intracellular cytokine staining assay. PBMCs will be stimulated in vitro with overlapping 15-mer peptide pools encoding the tumor-associated antigens CEA, MUC1, and Brachyury. Control peptide pools will involve the use of human leukocyte antigen peptide as a negative control and CEFT peptide mix as a positive control. CEFT is a mixture of peptides of CMV, Epstein-Barr virus, influenza, and tetanus toxin. Post-stimulation analyses of CD4 and CD8 T cells

will involve the production of IFN- γ , IL-2, tumor necrosis factor, and CD107a. If sufficient PBMCs are available, assays may also be performed for the development of T cells to other tumor-associated antigens. A detailed description of this assay has been previously reported (35).

2. If sufficient PBMCs are available, PBMCs from selected subjects may be analyzed for changes in standard immune cell types (CD4 and CD8 T cells, natural killer [NK] cells, regulatory T cells [Tregs], myeloid-derived suppressor cells [MDSCs], and dendritic cells) as well as 123 immune cell subsets, as described elsewhere (74), and for function of specific immune cell subsets, including CD4 and CD8 T cells, NK cells, Tregs, and MDSCs.

Analyses of soluble factors:

Sera will be analyzed pre- and post-therapy for the following soluble factors: sCD27, sCD40 ligand, and selected patients may be analyzed for cytokines and antibodies to human tumor antigens. For selected patients, sera may be analyzed for antibodies to CEA, MUC1, or Brachyury and adenovirus.

Additional assays:

Blood samples may be used for additional research studies, which may include phenotypic and functional analysis of immune-cell subsets and analyses for cytokines (IFN- γ , IL-10, IL-12, IL-2, IL-4, etc.), chemokines, antibodies, tumor-associated antigens, and/or other markers. In addition, assays for antibody or neutralizing antibody titer to adenovirus (type 5) and cell-mediated immunity to adenoviral antigens may be assessed.

Samples will be tracked according to Section 5.1.4.

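### The only inferential immune analysis in Section 8.4.9 compares dose levels, so it runs only after de-escalation and does not address whether vaccination generates T-cell responses

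*Combined protocol and SAP*

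**What the plan says.** The exploratory objective (Section 1.1.3) concerns the regimen's ability "to generate T-cell responses specific for Brachyury, MUC1, and CEA". The matching endpoint (Section 1.1.6) is induction of antigen-specific T cells, with serum sCD27 and sCD40L.

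Blood for immune assays is drawn at baseline, weeks 6, 14 and 30, and end of treatment (Section 5.1.1 and the study calendar). Section 5.1.6 has "Pre- and post-therapy PBMCs" assayed by intracellular cytokine staining after stimulation with CEA, MUC1 and Brachyury peptide pools.

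Section 8.4.9 then plans two descriptive summaries without any condition:
- "The magnitude of immune responses will also be described".
- "The percentage of subjects with a positive immune response will be evaluated by dose levels and overall enrollment".

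Inference is conditional: "If more than one dose level of patients is enrolled and at least three patients are treated in the dose level, Statistical analyses" will be done. The test is given in one sentence: "Student T tests will be performed on percentages of" TNF-α and/or IFN-γ "expressing cells among the different dose levels to determine any significant differences in cell populations". Section 8.4.9 mentions neither week 0 nor change from it, and names no sampling time for the test. Change from baseline appears in Section 8.4.4, for safety endpoints only.

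**The concern.** Three things do not fit together.

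- **The contrast.** Generating a response is a within-subject, before-and-after question. No objective or endpoint in Section 1.1 compares immune response between doses, yet that is the only comparison tested.
- **The condition.** The trial opens at one dose level. A second exists only if DLTs force de-escalation, so a trial that goes well never meets the condition.
- **The baseline.** Week-0 samples are taken and assayed but have no stated role in the analysis. They could matter: Section 2.1.1.8 admits subjects who stopped a vaccine against any of the three antigens as little as four weeks earlier, and Section 1.2.2 reports Brachyury-reactive T cells in patients vaccinated against other antigens. Dose levels also fill one after the other, so a difference in starting values between them could look like a dose effect.

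At stake is whether the trial can say, with a stated degree of uncertainty, that vaccination raised the T-cell response. Section 8.2 gives immunogenicity as one of the two reasons for the four expansion subjects.

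**Working it through.** **The plan's own figures.** Section 8.2: 6 + 4 = 10 subjects at the MTD, and 12 + 4 + 16 screen failures = 32 enrolled. Both reproduce. The documents give no alpha, power, SD or effect size for the immune analysis, so two-sided 5% and 80% power are assumed below.

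**Step 1: how often the test's condition can be met.** A second level needs at least 2 DLTs among 6 (Sections 3.1.2 and 8.2). Stopping at 2 of the first 3 is already contained in that event. With true DLT rate p,

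P(second level opens) = 1 − (1−p)^6 − 6p(1−p)^5.

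| Assumed p | (1−p)^6 | 6p(1−p)^5 | Second level opens | No test |
|---|---|---|---|---|
| 5% | 0.735 | 0.232 | 3.3% | 96.7% |
| 10% | 0.531 | 0.354 | 11.4% | 88.6% |
| 20% | 0.262 | 0.393 | 34.5% | 65.5% |
| 33% | 0.090 | 0.267 | 64.2% | 35.8% |

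Sections 1.2.6.1 and 11.1.2 report no DLT with ETBX-011 alone, which points to the upper rows. The combination is untested in humans, so p remains an assumption.

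**Step 2: what the test says about the objective when it runs.** In 40,000 simulated trials (6 and 10 subjects per level, pre/post correlation 0.7, equal effect at both levels), vaccination raised every subject by 0, 1 or 2 between-subject SDs. The dose-level t test rejected in 5.0%, 4.9% and 5.0% of trials. A paired t test in the 10 subjects rejected in 4.9%, 95.2% and 100%. An effect common to both levels cancels out of the planned contrast.

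**Step 3: what a paired analysis could detect.** For a paired t test (noncentral t):
- 10 pairs: 80% power at a mean change of 1.00 SD of the within-subject change.
- 8 pairs: 1.16 SD.
- 6 pairs: 1.43 SD.

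Ten is a maximum. Section 8.4.9 requires at least three injections for evaluability, and subjects leave for progression or DLT. In the earlier ETBX-011 trial 28 of 34 received all three treatments. At that rate, 10 × 28/34 ≈ 8.

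Power for a rise of one between-subject SD depends on the pre/post correlation r, because the SD of the change is √(2(1−r)) between-subject SDs. With 10 pairs it is 66%, 80%, 95% and 99% at r = 0.3, 0.5, 0.7 and 0.8. The documents give no r.

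**Step 4: how many tests.** Four post-baseline draws × three antigens = 12. Unadjusted, and if independent, the chance of at least one false positive is 1 − 0.95^12 = 46%. With one time point and three antigens it is 1 − 0.95^3 = 14%. The smallest two-sided exact signed-rank p is 2/2^n: 0.002 at n = 10, 0.008 at n = 8 and 0.031 at n = 6. A Bonferroni threshold of 0.05/3 = 0.017 is attainable with 8 or 10 pairs, but not with 6.

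**Step 5: comparing two levels, if both exist.** For a dose difference of 1 SD with 6 versus 10 subjects, the test on post-vaccination values has 44% power. A test on change scores has 33%, 44%, 64% and 81% at r = 0.3, 0.5, 0.7 and 0.8. Change scores gain only when r exceeds 0.5.

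**The case against.** The strongest defence is that this is an exploratory aim in about ten subjects with mixed tumours, and Section 8.4.1 sets a descriptive approach throughout. Magnitude and percent positive are reported even with a single dose level, and these bear on the objective. That stands. A reader might infer that no immune analysis is planned unless de-escalation occurs; the two unconditional summaries rule that out. They do not close the gap, however. Neither has a stated interval, and neither is defined relative to week 0. The positivity rule is a count above background, and the source it cites cannot be checked here.

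A reader might also infer that the plan discards baseline or tests raw values by design. The documents do not support this either. Section 8.4.9 is silent on week 0, Section 5.1.6 assays pre-therapy samples, and nothing prevents their use.

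Two quantitative readings should be resisted. One is that ten subjects will have paired samples; ten is the ceiling. The other is that a paired test needing 1.0 SD beats a between-level test needing 1.56 SD (6 versus 10). The first figure is in SDs of within-subject change and the second in between-subject SDs, and the hypotheses differ. The case rests on the contrast tested, not on that comparison.

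Finally, a paired test at every time point for every antigen would bring its own multiplicity problem (Step 4). That is right, and it narrows the fix.

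**Conclusion.** The point holds in this form: Section 8.4.9 describes immune response unconditionally, but its only inferential analysis is aimed at a contrast that is not an objective. It becomes available with probability 3%, 11% or 34% at assumed DLT rates of 5%, 10% or 20%, and it leaves time point and baseline handling unstated. If the true DLT rate were as high as 33%, the test would become available more often than not (64%), but it would still not address induction.

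The weight is moderate. No safety, MTD or secondary efficacy conclusion depends on it, and the samples needed for a better analysis are already in the schedule. It would be too strong to say that the between-level test can never separate dose from baseline. What can be said is that the plan states no step to do so, and that adjusting for week 0 would not remove confounding from sequential, non-randomised enrolment.

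**What to change.** In Section 8.4.9:

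- Whatever the number of dose levels, analyse magnitude as within-subject change from week 0 for each of the three antigens at one pre-named main time point. Week 14 is an example: draws precede injections, so it is the first scheduled draw after all three initial vaccinations.
- Report the median change with an interval and a Wilcoxon signed-rank test in subjects with paired samples (at most 10 at the MTD), giving the number of pairs.
- Describe the other time points without testing.
- Label all results exploratory, and either adjust across the three antigens or state that no adjustment is made.
- If two dose levels are compared, adjust for the week-0 value, report the comparison descriptively, and note that enrolment was sequential and not randomised.

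The cost is SAP wording and slightly more analysis, with no new samples or assays. Precision stays limited: before any multiplicity adjustment, 80% power needs about 1.0 SD of within-subject change with 10 pairs and about 1.16 SD with 8. Those figures are for a paired t test and serve only as a guide for the signed-rank test.

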9 COLLABORATIVE AGREEMENTS

9.1 COOPERATIVE RESEARCH AND DEVELOPMENT AGREEMENT (CRADA)

A CRADA is in place between the Laboratory of Tumor Immunology and Biology (LTIB), CCR NCI and Etubics Corporation, the manufacturer of ETBX-011 (adenoviral CEA vaccine); ETBX-061 (adenoviral MUC1 vaccine); and ETBX-051 (adenoviral brachyury vaccine), CRADA# 02997.

10 HUMAN SUBJECTS PROTECTIONS

10.1 RATIONALE FOR SUBJECT SELECTION

10.1.1 Selection Based on Gender, Ethnicity, and Race

Subjects from all genders and racial/ethnic groups are eligible for this study if they meet the eligibility criteria. To date, there is no information that suggests that differences in drug metabolism or disease response would be expected in one group compared with another. Efforts will be made to extend accrual to a representative population, but in this preliminary study, a balance must be struck between patient safety considerations and limitations on the number of individuals exposed to potentially toxic and/or ineffective treatments on one hand and the need to explore gender and ethnic aspects of clinical research on the other hand. If differences in outcome that correlate with gender and ethnic identity are noted, accrual may be expanded or a follow-up study may be written to investigate those differences more fully.

10.1.2 Strategies/Procedures for Recruitment

Patient accrual for this protocol will be facilitated by Web-based recruitment strategies. This protocol will be listed on www.clinicaltrials.gov.

10.1.3 Justification for Exclusions

Due to impaired cellular immunity with the concomitant increased risk of serious side effects from vaccinations with infectious agents, the Centers for Disease Control and Prevention recommends that HIV infected patients be excluded, in addition, patients with chronic hepatitis infection, including B and C, because of potential immune impairment.

10.2 PARTICIPATION OF CHILDREN

Because no dosing or adverse event data are currently available on the use of the study vaccines in patients <18 years of age, children are excluded from this study.

10.3 PARTICIPATION OF SUBJECTS UNABLE TO GIVE CONSENT

Adults unable to give consent are excluded from enrolling in the protocol. However, re-consent may be necessary and there is a possibility, though unlikely, that subjects could become decisionally impaired. For this reason and because there is a prospect of direct benefit from research participation (section 10.4), all subjects \geq age 18 will be offered the opportunity to fill in their wishes for research and care, and assign a substitute decision maker on the “NIH Advance Directive for Health Care and Medical Research Participation” form so that another person can make decisions about their medical care in the event that they become incapacitated or cognitively impaired during the course of the study. Note: The PI or AI will contact the NIH Ability to Consent Assessment Team for evaluation. For those subjects that become incapacitated and do not have

pre-determined substitute decision maker, the procedures described in MAS Policy 87-4 for appointing a surrogate decision maker for adult subjects who are (a) decisionally impaired, and (b) who do not have a legal guardian or durable power of attorney, will be followed.

10.4 EVALUATION OF BENEFITS AND RISKS/DISCOMFORTS

Patients will receive evaluation of their disease at the National Cancer Institute's Clinical Center. This protocol may or may not benefit an individual, but the results may help the investigators learn more about the disease and develop new treatments for patients with this disease.

Potential adverse reactions attributable to the administration of the vaccine utilized in this trial are discussed in section 11. All care will be taken to minimize side effects, but they can be unpredictable in nature and severity. Patients will be examined and evaluated prior to enrollment. All evaluations to monitor the treatment of patients will be recorded in the patient chart. If patients suffer any physical injury as a result of the participation in this study, immediate medical treatment is available at the Clinical Center, National Cancer Institute, Bethesda, Maryland.

Although no compensation is available, any injury will be evaluated and treated in keeping with the benefits or care to which patients are entitled under applicable regulations. In all publications and presentations resulting from this trial, patients' anonymity will be protected to the maximum extent possible. Authorized personnel from the National Cancer Institute (NCI) and Food and Drug Administration (FDA) or other regulatory authorities may have access to research files in order to verify that patients' rights have been safeguarded. In addition, patient names will be given to the Central Registration to register and verify patients' eligibility.

10.5 CONSENT PROCESS AND DOCUMENTATION

The investigational nature and research objectives of this trial, the procedures and treatments involved and their attendant risks and discomforts and benefits, and potential alternative therapies will be carefully explained to the patient, and a signed informed consent document will be obtained by a study investigator prior to entry onto the study.

The PI or associate investigator will meet with the patient to discuss the protocol treatment and alternative options in detail. It will be stated clearly that participation in the research study is voluntary and that participants can withdraw from the study without losing benefits they would otherwise be entitled to. The patient will be encouraged to ask questions, and additional meetings to discuss the treatment options will be arranged as necessary.

If there is an optional biopsy for research in the protocol, then the patient will consent at the time of the procedure. If the patient refuses the optional biopsy at that time, the refusal will be documented in the medical record.

10.5.1 Telephone re-consent procedure

Re-consent on this study may be obtained via telephone according to the following procedure: the informed consent document will be sent to the subject. An explanation of the study will be provided over the telephone after the subject has had the opportunity to read the consent form. The subject will sign and date the informed consent. A witness to the subject's signature will sign and date the consent. The original informed consent document will be sent back to the consenting

investigator who will sign and date the consent form with the date the consent was obtained via telephone. A fully executed copy will be returned via mail for the subject's records. The informed consent process will be documented on a progress note by the consenting investigator.

10.5.2 Consent process for non-English speaking subjects

If there is an unexpected enrollment of a research participant for whom there is no translated extant IRB approved consent document, the principal investigator and/or those authorized to obtain informed consent will use the Short Form Oral Consent Process as described in MAS Policy M77-2, OHSRP SOP 12, 45 CFR 46.117 (b) (2), and 21 CFR 50.27 (b) (2). The summary that will be used is the English version of the extant IRB approved consent document. Signed copies of both the English version of the consent and the translated short form will be given to the subject or their legally authorized representative and the signed original will be filed in the medical record.

Unless the PI is fluent in the prospective subject's language, an interpreter will be present to facilitate the conversation. Preferably someone who is independent of the subject (i.e., not a family member) will assist in presenting information and obtaining consent. Whenever possible, interpreters will be provided copies of the relevant consent documents well before the consent conversation with the subject (24 to 48 hours if possible).

We request prospective IRB approval of the use of the short form process and will notify the IRB at the time of continuing review of the frequency of the use of the Short Form.

11 PHARMACEUTICAL INFORMATION

11.1 COMBINATION ETBX-011, ETBX-051, ETBX-061 VACCINE REGIMEN

The combination ETBX-011, ETBX-051, ETBX-061 vaccine regimen refers to the combination of three investigational adenoviral vaccines. All utilize the same second generation E1(-), E2 (-) vector. Subjects will each receive the three vaccines at the same time, at the same doses, through three separate injections administered in different limbs (proximal limb areas) or separate locations.

ETBX-011 is a CEA-targeting vaccine that comprises the Ad5 [E1-, E2b-] vector and a modified CEA (CEA(6D)) gene insert. The investigational product ETBX-061 is a MUC1-targeting vaccine that comprises the Ad5 [E1-, E2b-] vector and a modified MUC1 (MUC1c) gene insert. The investigational product ETBX-051 is a Brachyury-targeting vaccine that comprises the Ad5 [E1-, E2b-] vector and a modified Brachyury gene insert. (**Table 8**). Refer to the current version of the Investigator's Brochure for detailed investigational product information.

Table 8: Investigational Products

Table 8a

Product Name(s):	ETBX-011 (Ad5 [E1-, E2b-]-CEA(6D) Vaccine)
Dosage Form:	Suspension for injection

Dose	5 x 10 ¹¹ VP (standard dose), or 1 x 10 ¹¹ VP (DL-1).
Route of Administration	SC injection
Physical Description	ETBX vaccine is supplied as a sterile, clear solution in a 2-mL single-dose vial. The vaccine is provided at a concentration of 5 x 10 ¹¹ VP per 1 mL and contains ARM formulation buffer (20 mM TRIS, 25 mM NaCl, 2.5% glycerol, pH 8.0). Each vial contains approximately 1.3 mL of the vaccine. The product should be stored at -20+10°C until ready for use.
Manufacturer	Etubics

Table 8b

Product Name(s):	ETBX-061 (Ad5 [E1-, E2b-]-MUC1 Vaccine)
Dosage Form:	Suspension for injection
Dose	5 x 10 ¹¹ VP (standard dose), or 1 x 10 ¹¹ VP (DL-1).
Route of Administration	SC injection
Physical Description	ETBX vaccine is supplied as a sterile, clear solution in a 2-mL single-dose vial. The vaccine is provided at a concentration of 5 x 10 ¹¹ VP per 1 mL and contains ARM formulation buffer (20 mM TRIS, 25 mM NaCl, 2.5% glycerol, pH 8.0). Each vial contains 1 mL of extractable vaccine. The product should be stored at ≤ -60°C until ready for use.
Manufacturer	Etubics

Table 8c

Product Name(s):	ETBX-051 (Ad5 [E1-, E2b-]-Brachyury Vaccine)
Dosage Form:	Suspension for injection
Dose	5 x 10 ¹¹ VP (standard dose), or 1 x 10 ¹¹ VP (DL-1).
Route of Administration	SC injection
Physical Description	ETBX vaccine is supplied as a sterile, clear solution in a 2-mL single-dose vial. The vaccine is provided at a concentration of 5 x 10 ¹¹ VP per 1 mL and contains ARM formulation buffer (20 mM TRIS, 25 mM NaCl, 2.5% glycerol, pH 8.0). Each vial contains 1 mL of extractable vaccine. The product should be stored at ≤ -60°C until ready for use.
Manufacturer	Etubics

